An adverse event (AE) is defined as any unfavorable and unanticipated sign (including an abnormal laboratory finding), symptom, or disease temporally associated with the use of a study procedure(s), whether or not it is related to the study procedure(s). The intensity of all AEs is classified as follows:

- *Mild*: A mild AE is defined as an event characterized by "awareness of symptoms which are easily tolerated."
- *Moderate*: A moderate AE is defined as an event in which "sufficient discomfort is present to cause interference with usual activity."
- *Severe*: A severe AE is defined as an event characterized by "extreme distress causing significant impairment of function or incapacitation."
- A *Serious Adverse Event (SAE)* is any AE occurring at any dose that results in:
 - Death.
 - A life-threatening event.
 - Inpatient hospitalization or prolongation of existing hospitalization.
 - Persistent or significant disability/incapacity.
 - Congenital anomaly/birth defect.

In addition, an important medical event that may not result in death, be life-threatening, or require hospitalization may be considered a SAE when, based on appropriate medical judgment, it may jeopardize the individual and/or may require medical or surgical intervention to prevent one of the outcomes listed above.

An *Unexpected AE* is any AE of which the specificity or severity is not consistent with that expected or anticipated as possible from administration of the study procedure.

A *Reasonably Related AE* is one that is possibly probably or definitely related to the study procedure (as determined by the study investigator).

REASONABLY ANTICIPATED AND POTENTIAL ADVERSE EVENTS

SAEs are not anticipated to occur in this clinical study.

Reasonably anticipated and potential AEs that may occur in this clinical study include the following:

- *Anticipated Adverse Event*: None observed or reported to date in prior clinical trials.
- *Potential Adverse Events*: include skin irritation, itching, discoloring, rash, indentations, pain/discomfort and infection.

EVALUATION OF ADVERSE EVENTS

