At each evaluation and procedure administration test site visit throughout the clinical study, and at any other time throughout the duration of the clinical trial that is necessary, evaluation for the occurrence of any potential adverse event will occur. This includes any observations made by the study investigator or other study staff or any reports made by the subject. Subjects will be instructed as to what constitutes an adverse event and how to report any potential adverse event(s) he or she may identify during study participation to the test site. The subject will be instructed to formally evaluate for potential adverse events through their recordings in their Subject Daily Diary completed at home.

RECORDING OF ADVERSE EVENTS

AEs that occur after randomization are recorded by the Principal Investigator on the AE page of the CRF. Recording is done in a concise manner using standard, acceptable medical terms. Any clinically significant changes in pre-existing conditions (based on medical history/physical examination results) are recorded on the CRF AE pages.

REPORTING OF ADVERSE EVENTS

The investigator will notify the Sponsor right away of any identified or reported adverse event, whether determined by the investigator to be related or unrelated to the study treatment or device or whether it is an anticipated or unanticipated AE. The investigator and the Sponsor will determine if the AE is a promptly reportable event to the governing IRB. The investigator will formally report any serious, life-threatening, or unexpected adverse experiences, including death that occurs within the duration of this study regardless of the relationship to the study procedure.

PROTOCOL DEVIATIONS AND VIOLATIONS

Both protocol deviations and protocol violations are accidental or unintentional changes to, or non-compliances with, the IRB-approved research protocol without prior sponsor and IRB approval. The difference between the two lies in the level of risk introduced by the change.

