Positive blinding efficacy will be supported by comments provided to support perceived group allocation that pertain to the determination being made based on treatment efficacy or lack thereof; e.g.: 'My foot pain is much less than it used to be, so I believe I got the real treatment' or 'My foot pain hasn't really changed, so I believe I got the fake treatment.'

Blinding will be determined to have failed if comments provided to support perceived group allocation pertain to factors such as sensation/visual clues (e.g. I saw/didn't see a light go on the laser, etc.) or other factors that pertain to blinding having been compromised such as 'I overheard the doctor saying I wasn't getting the real treatment.'

SAFETY ANALYSES

Safety analyses will be based on all subjects who were randomized to test or placebo procedure group. Safety will be assessed by evaluating and comparing frequency and incidence of observed and/or reported adverse events between test and placebo procedure groups related to administration of the Erchonia® FX-635™ laser procedures. A chi-square test with a continuity correction will be performed to compare the percentage of subjects who experienced adverse events between test and placebo procedure group subjects.

INDIVIDUAL SITE ANALYSIS

Analysis of results will be performed by individual test site and pooled across test sites. Application of a balanced test-control group study design incorporating a varied block by test site randomization procedure will contribute to statistical justification of pooling data across the different test sites.

INFORMED CONSENT

- Informed consent will be an agreement between the individual investigator and each subject, having the capacity to understand and make an informed decision. Consent will be obtained prior to each potential subject's participation in this clinical study.
- Each subject participating in this clinical study will be made aware of the fact that his or her participation involves research and the intent of the research, the expected duration of his or her participation and a description of the procedures that will be followed.
- Each subject will be made aware of the reasonably expected benefits he or she might receive, as well as any risks or potential discomfort that are involved.
- Each subject will also be made aware of alternative treatments available to him or her.

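### The Safety Analyses section conflicts on relatedness: one sentence compares only events related to the laser procedures, the test sentence sets no such limit, and the plan does not say which set counts.

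*Combined protocol and SAP*

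**What the plan says.** The Safety Analyses section of the combined protocol and SAP fixes the population first: "Safety analyses will be based on all subjects who were randomized to test or placebo procedure group". Two sentences on the comparison follow.

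- The first says how safety is assessed: by comparing "frequency and incidence of observed and/or reported adverse events between test and placebo procedure groups related to administration of the" FX-635 laser procedures.
- The second gives the test: "A chi-square test with a continuity correction will be performed to compare the percentage of subjects who experienced adverse events between test and placebo" subjects. It does not mention relatedness.

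Elsewhere the protocol handles AEs without regard to cause:

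- **Adverse Events Definition:** an AE counts "whether or not it is related to the study procedure(s").
- **Recording of Adverse Events:** "AEs that occur after randomization are recorded by the Principal Investigator on the AE page of the CRF". No relatedness condition is attached.
- **Reporting of Adverse Events:** the sponsor is to be told of any AE, related or not.
- **Secondary Efficacy Outcome Measures:** the items to be explored include adverse events, unqualified.

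Relatedness has its own term in the Adverse Events Definition section. A reasonably related AE "is one that is possibly probably or definitely related to the study procedure (as determined by the study investigator"). The Safety Analyses section does not use that term.

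**The concern.** In a randomized sham-controlled trial, the difference between arms in all adverse events is the evidence on whether the device causes harm. It does not depend on anyone's judgement of the individual case. If events are first filtered by a judgement of relatedness, part of that evidence is lost before the arms are compared.

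The qualifier in the first sentence invites such a filter. The only rule for relatedness that the protocol offers is the one made "as determined by the study investigator". Two features of the protocol could push that judgement towards unrelated:

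- The list of anticipated AEs reads "None observed or reported to date in prior clinical trials", and the Study Rationale & Justification section presents the therapy as having no side effects.
- Some listed potential events, such as pain or discomfort and infection, overlap with symptoms and complications that the protocol ascribes to diabetic neuropathy itself.

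Two analysts could follow the section in good faith and produce different safety tables. Because the plan does not choose, the choice could be made once the results are known. The trial is meant to support a 510(k) submission, and this section holds its only planned between-arm safety test.

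**Working it through.** **Step 1. Set the wording side by side.**

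| Place | Events covered |
|---|---|
| Safety Analyses, first comparison sentence | Related to the laser procedures |
| Safety Analyses, chi-square sentence | AEs, no limit stated |
| Adverse Events Definition | Related or not |
| Recording of Adverse Events | After randomization, no relatedness condition |
| Reporting of Adverse Events | Related or not |
| Secondary Efficacy Outcome Measures, items to be explored | AEs, no limit stated |

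The first row is the exception. With the protocol's own definition of an AE, the chi-square sentence gives an all-cause comparison. Read as the continuation of the sentence before it, the same test covers related events only. Nothing in the section settles which is meant.

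**Step 2. Can the reading change the result?** The plan states no figure for the safety comparison, so there is none to reproduce. The one documented input is 32 subjects per group (Sample size section); all randomized subjects enter the safety analysis. The counts below are assumptions. They treat attribution at subject level and apply the same share judged related in both arms.

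With a and b subjects affected out of n = 32 per arm, and N = 64, the continuity-corrected statistic is

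X² = N(|a(n − b) − b(n − a)| − N/2)² / [(a + b)(N − a − b)n²], on 1 degree of freedom.

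For 12 versus 4:

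- a(n − b) − b(n − a) = 12 × 28 − 4 × 20 = 256
- 256 − 32 = 224
- X² = 64 × 224² / (16 × 48 × 32²) = 4.08, p = 0.043

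For 3 versus 1:

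- 3 × 31 − 1 × 29 = 64
- 64 − 32 = 32
- X² = 64 × 32² / (4 × 60 × 32²) = 0.27, p = 0.61

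The same formula over a range of shares, starting from 12 versus 4 with any AE:

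| Share judged related | Active vs sham | Difference | X² | p |
|---|---|---|---|---|
| All events counted | 12/32 vs 4/32 (37.5% vs 12.5%) | 25.0 points | 4.08 | 0.043 |
| Three quarters | 9/32 vs 3/32 (28.1% vs 9.4%) | 18.8 points | 2.56 | 0.11 |
| One half | 6/32 vs 2/32 (18.8% vs 6.3%) | 12.5 points | 1.29 | 0.26 |
| One quarter | 3/32 vs 1/32 (9.4% vs 3.1%) | 6.3 points | 0.27 | 0.61 |

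The absolute excess shrinks in proportion to the share: 25 points × 1/4 = 6.25 points.

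**Step 3. A second starting point.** With 10 versus 3 subjects (31.3% versus 9.4%, 21.9 points), the all-cause test gives X² = 64 × (224 − 32)² / (13 × 51 × 32²) = 3.48, p = 0.062. If about a third are judged related, this again becomes roughly 3 versus 1. Here the all-cause test misses 5% as well, so the reading changes the size of the reported excess but not the side of the threshold.

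**The case against.** A reader might infer from the first sentence that the safety comparison covers related events alone, so that an unattributed excess in the active arm would not count. The documents do not support that. The only formal test is on subjects with adverse events, without restriction, and the defined meaning of that term includes unrelated events. Recording, sponsor notification and the list of items to be explored all point the same way. On the plainest reading of the test sentence, such an excess would count.

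A reader might also infer that the investigator's attribution is the stated filter. It is not. The Safety Analyses section never uses the defined term for related AEs, and the phrase may be only a loose echo of the temporal association in the AE definition. The link to investigator judgement is an inference, made because no other relatedness rule exists.

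Three further points reduce the likely harm:

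- Related includes possibly related, which is a low bar.
- Investigators are told of seven kinds of potential event, including pain or discomfort and infection, so they are not simply primed to expect nothing.
- The planned blinding means attribution should not favour one arm. A filtered comparison loses information but need not hide an excess completely; the example still shows 3 versus 1.

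All of this stands against the stronger claims. It does not remove the inconsistency: the sentence that says how safety is assessed carries a limit that the test sentence and the definition lack. Nor does blinding cure the loss, since equal under-attribution in both arms still shrinks the absolute difference.

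**Conclusion.** The concern holds as an inconsistency within the Safety Analyses section, not as a proven exclusion of events. The first comparison sentence is narrower than the chi-square sentence, the AE definition and the data collection, and the plan does not say which governs. Under the restrictive reading, an excess not attributed to the device could drop out of the between-arm comparison; under the other reading it is counted.

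No stated figure is wrong. The size rests on assumed counts and attribution shares for which the documents give no source. With 32 per arm and an assumed 12 versus 4, the excess ranges from 25 points (p = 0.043) with all events counted to 6.3 points (p = 0.61) with a quarter judged related. The 10 versus 3 example shows that the result need not cross 5%. Together they show that the choice of reading can matter, not that it will.

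**What to change.** In the Safety Analyses section:

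1. Delete the qualifier tying the compared events to administration of the laser procedures.
2. State that the between-arm comparison, including the chi-square test, covers all AEs after randomization regardless of attribution.
3. Add a secondary table by arm of reasonably related AEs, as defined in the Adverse Events Definition section.

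Tabulating each listed potential event by arm is optional; it is not needed to resolve the conflict.

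The cost is a wording change and one more table, from data the protocol already collects. If the restrictive reading was the intended one, the headline AE percentages will rise in both arms. The change should be made before unblinding, so that the choice of event set cannot depend on the results.
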